3.6 HIPAA Authorization

A partial HIPAA Waiver of Authorization will be requested to enable thorough screening for eligibility. This process involves no more than a minimal risk to subjects' privacy because identifiers will be collected in a secure way and destroyed after the study is closed. In addition, the protected health information collected will not be reused or disclosed to any other person or entity other than the research team, except as required by law. Because we aim to enroll participants within a specific window of maintenance therapy, we have a relatively narrow timeframe in which to identify eligible participants. Without such a waiver, we would have to rely solely on provider-generated referrals or patient and parent self-referral, which would add an undue burden to pediatric hematology/oncology providers and potentially lead to such slow participant accrual that the research would be rendered infeasible. Alternatively, requesting consent from each potential study participant prior to review of preliminary eligibility would result in an unnecessary burden for families.

We will review the participant's medical records for documentation of any discussion related to sleep during routine (non-emergency) JFC clinic appointments for the 12-week period prior to and following the ONN baseline visit at study. To obtain permission for the medical record abstraction portion of the study, we will have participants provide a signature for HIPAA Authorization. As we wish for documented consent to be waived, the HIPAA authorization form will be a standalone document. Signed HIPAA authorization will be obtained in person alongside the verbal consent.

3.7 Strategies for Retention

We will actively retain families in this study by utilizing ongoing study team contact to maintain engagement as well as modest remuneration for participation. Families enrolled will receive small remuneration to off-set the cost of their time participating in the baseline and intervention assessment (\$20 gift-card at baseline and a \$40 gift-card for the intervention assessment). Due to the relatively low-participant burden, modest remuneration, and patient-centered nature of the intervention we do not anticipate problems with recruitment and retention.

4. REGISTRATION PROCEDURES

4.1 Registration Process for DF/HCC Institutions

A member of the study team will confirm eligibility criteria and complete the protocol-specific eligibility checklist. Institutions will register eligible participants in the Clinical Trials Management System (CTMS) OnCore as required by DF/HCC Policy REGIST-101.

4.2 General Guidelines for Other Investigative Sites

N/A.

4.3 Registration Process for Other Investigative Sites

N/A.

5. STUDY DESIGN

5.1 Overall Study Design

We will conduct a single arm, pilot acceptability and feasibility study of the sleep intervention (Sleep ALL Night).

Intervention Structure: As pediatric cancer services are centralized, travel burden for clinical care is a treatment barrier.¹⁰ It is important that the program content be accessible for those who do not live near an academic medical center. While this does not address all family-level obstacles to accessing sleep care, this is a vital first step. Further, we recognize that parents of pediatric cancer patients are overwhelmed and exhausted from the many medical appointments their child has had during treatment^{11,12} As adherence to multi-session sleep interventions is poor in pediatric oncology¹³ and we have previously demonstrated that a brief psychoeducational program is efficacious¹⁴ we plan to implement a sleep action plan tool, in conjunction with an interactive psychoeducational website. Enrollment in the intervention will take place at the initial visit with the ONN and will be followed by the Intervention Survey (administered at Week-3) and the overall website monitoring that will occur from Week 1 up until Week 12 (end of study).

The sleep action plan will be presented on a single page (Appendix B), resembling action plans that are commonly implemented for children with other chronic medical conditions (e.g., asthma).¹⁵ The action plan is separated into three ‘zones’: 1) a green zone, indicating that the child is sleeping well, reminding families that sleep is something to monitor; 2) a yellow zone, indicating that the child’s sleep is worsening, encouraging families to begin tracking their child’s sleep; and 3) a red zone, indicating that the child’s sleep is problematic, providing concrete steps to take in order to initiate further evaluation and any necessary treatment(s).

[figure not shown]
ONNs will introduce families to the sleep action plan immediately after study enrollment. Spanish interpreters will aid ONNs in explaining the sleep action plan to Spanish speaking caregivers. If this is not a feasible time to meet with the families, (i.e., someone has to leave right after enrollment), the study team will coordinate a time for the family meet with the ONN at the time of their next in person visit. ONNs will explain that if they are interested in further information regarding their child’s sleep, that they should review the intervention website. On

the website, families will be provided with comprehensive information on how to successfully navigate the many potential disruptors of their child's sleep as they complete maintenance therapy. Feedback will be solicited through an Intervention survey (administered at Week-3) focused on the acceptability and feasibility of the intervention materials and delivery format for a family of a child with cancer. These materials are based on the American Academy of Sleep Medicine's clinical guidelines for managing disordered sleep, and child and family feedback that was provided during Phase 1 of this project. Data collection will occur over 3 months via the intervention website and during the intervention survey (administered at Week-3). To maximize data collection, families will preferably complete the intervention survey (administered at Week-3) in-person via REDCap or paper/pencil. However, surveys may also be completed using alternative methods, including, but not limited to, REDCap link texted/mailed to participants and phone/Zoom administration (read aloud by site personnel with answers recorded). Reminders to complete the survey will be sent as needed via various methods, including, but not limited to, emails, phone calls, and text messages. An Amazon gift card will also be sent to families as modest remuneration for their time completing the survey.

5.2 Study processes

Study procedures are designed to accommodate both in-person, fully remote, or hybrid approaches to consent, orientation, study conduct and data collection.

Screening for eligibility: Prior to approach for consent, eligible patients (see Inclusion Criteria) will be identified from existing DFCI 16-001 study databases and the Heme Malignancy clinical tracking system.

Data Collection:

All self-reported outcomes will be collected at Week 12 post-report.

Week 12
 End of Study Medical
 Record Abstraction

Acceptability

- Study staff: Number of eligible participants who are approached who agree to participate in the study. *Not administered to participants*
- Parent-completed survey: Self-report to single-items querying current level of concern about their child's sleep, and their interest in learning more about how to improve their child's sleep, on a 10-point scale. *Administered during the Baseline Assessment only*.
- Parent-completed survey: Acceptability of Intervention scale¹⁶. *Administered during the Intervention Assessment only*.

Feasibility

- Parent-completed survey: Self-report of frequency of reviewing the study action plan. *Administered during the Intervention Assessment only*.
- Parent-completed survey: Self-report of frequency of reviewing the study website. *Administered during the Intervention Assessment only*.
- Study Staff: Website tracking of frequency of access and time of day of access. *Not administered to participants*.
- Study Staff: Number of enrolled participants who complete the Intervention Assessment. *Not administered to participants*.

Program material feedback

- Parent-completed survey: Open-ended Intervention survey (administered at Week-3) regarding sleep action plan and website. *Administered at Intervention Assessment only*.

Program impact

- Parent-completed: Self-efficacy for Sleep scale (SES)¹⁷. The SES is a 9-item scale used to assess an individual's sense of self-efficacy with regards to sleep. Our modified version will ask parents to rate how confident they feel about helping their child accomplish a behavior, such as "lie in bed feeling mentally relaxed" or "Fall asleep at night in less than 30 minutes" on a 5-point scale, with higher scores reflecting greater self-efficacy relating to sleep. *Administered at Baseline (week 0) and Intervention (week 3) Assessment*.
- Parent-completed Patient-Reported Outcomes Measurement Information System (PROMIS) Sleep Disturbance and Sleep-Related Impairment.¹⁸ The PROMIS Sleep Disturbance and Sleep-Related Impairment scales are a 16-item measure used to assess the extent of a child's poor sleep and the consequences of their poor sleep *Administered at Baseline (week 0) and Intervention (week 3) Assessment*.
- Parent-completed Sleep Knowledge Scale. This scale is a 10-item scale designed to determine the extent of a parent's knowledge about sleep in children. *Administered at Baseline (week 0) and Intervention (week 3) Assessment*.
- Study Staff: CRC review of participant's medical records for documentation of any discussion related to sleep during routine (non-emergency) JFC clinic appointments for

the 12-week period prior to and following the ONN baseline visit at study enrollment.

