1.2 Primary Objectives

1. To evaluate the acceptability and feasibility of the Sleep ALL Night intervention in a single arm pilot study of N=30 pediatric patients with ALL.
 - a. Acceptability will be defined as (1) $\geq 30\%$ of eligible participants who are approached agree to participate, and (2) participants report an average score ≥ 4 ("Agree") on the Acceptability of Intervention Measure scale.⁸
 - b. Feasibility will be defined as: (1) $\geq 70\%$ of participants report reviewing the study

action plan, (2) ≥50% of participants report accessing the psychoeducational website, and (3) ≥80% of participants complete the Intervention Assessment.

2. To refine the program materials based on participant feedback.
3. To collect preliminary data assessing the impact of the program on increasing frequency of sleep health conversations during Jimmy Fund Clinic medical appointments based on electronic medical record review of clinic notes and parent survey response.

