5.6 Duration of Follow Up

Participants will be followed for 3-weeks after their initial ONN baseline visit for the Intervention survey; and a total of 12 weeks for any website activity.

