11.5 Analysis of Primary Endpoints

Patient sociodemographic, disease, and treatment characteristics will be analyzed with descriptive statistics.

Primary study outcomes of acceptability and feasibility will be assessed based on the Implementation Outcomes Framework and best practice metrics for clinical trials.^{19,20} The study will be deemed acceptable if: (1) $\geq 30\%$ of eligible participants who are approached agree to participate, and (2) participants report an average score ≥ 4 (“Agree”) on the Acceptability of Intervention Measure scale. The study will be deemed feasible if: (1) $\geq 70\%$ of participants report reviewing the study action plan, (2) $\geq 50\%$ of participants report accessing the psychoeducational website, and (3) $\geq 80\%$ of participants complete the Intervention Assessment.

Primary study outcomes (Self-efficacy for Sleep and Patient-Reported Outcomes Measurement Information System Sleep Disturbance and Sleep-Related Impairment total scores; proportion of routine visits with a discussion of sleep pre/post ONN baseline visit) will be presented descriptively.

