“We want families to talk with us as soon as they think their child’s sleep is in the yellow zone or worse. It doesn’t necessarily mean that anything needs to be done, but it means that now your child’s medical team will keep sleep at the top of their mind in case we need to do something differently to help them sleep and feel better. Does this make sense?”

“Have you ever used a QR code before? At the bottom right of this Sleep Action Plan, you will see one. Point your phone or tablet camera and a link appears.

Show how to do on patient’s phone, if available; otherwise show on ONN phone

Tap this link and it will take you to our special website. I suggest that you take a look at this website in the next few days, even if sleep is going well for your family. It provides a lot of really good information about what is normal for a child’s sleep, what issues to look out for, and tips and strategies that can help your family deal with any sleep issues.”

Navigate to Sleep Diary calculator on website. Show physical Sleep Diary.

“This is a Sleep Diary, which is a tool that may be helpful for your family to use to get a sense of how your child is sleeping on average. What you will want to do is follow the instructions on the sleep diary to track their sleep for about a week, then enter that information into this online calculator, which will give you some key sleep facts that .”

“That’s it! We’re hoping that this can be something you put on your fridge, so that it can remind you of what to keep a lookout for when it comes to sleep issues. Do you have any last questions?”

13.4 Appendix D. Sleep Study Invitation Email/Letter.

Dear <name>,

We are contacting you because you may be eligible to participate in a research study we are conducting to better understand how we can help families navigate potential sleep problems for children during medical treatment. Your child's doctor is aware of this study and has agreed for his/her patients and their families to be contacted.

Your and/or your child's participation would include:

- Completing a brief, baseline survey (about 10 minutes)
- Talking with an oncology nurse navigator for 5-10 minutes about informational materials that are available to help families understand sleep during treatment for acute lymphoblastic leukemia
- Completing a brief intervention survey (about 10 minutes)

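### The ≥50% website criterion rests on parent self-report alone; the 12-week website log, with no described link to families and no planned analysis, cannot check it as described

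*Combined protocol and SAP*

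**What the plan says.** All references are to the combined protocol and SAP.

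- **Criterion.** Sections 1.2 and 11.5 set three feasibility conditions. The second is "≥50% of participants report accessing the psychoeducational website".
- **Source of the criterion.** Section 5.2 gives the parent survey item as "Self-report of frequency of reviewing the study website", asked only at the Intervention Assessment. Sections 5.1 and 5.6 place that assessment at Week 3, as do several items in 5.2. One sentence at the head of the data-collection list in 5.2 instead puts every self-reported outcome at Week 12.
- **Mode.** Section 5.1 prefers in-person completion on REDCap or paper. It also allows staff to read the questions out by phone or Zoom.
- **Objective measure.** Section 5.2 lists "Website tracking of frequency of access and time of day of access" under Feasibility, as a staff-collected item. Section 5.6 follows participants for "a total of 12 weeks for any website activity".
- **Route to the site.** The action plan and sleep diary (Appendix B) print a single web address. The nurse navigator script (Appendix C) points to a QR code on the plan and continues: "Tap this link and it will take you to our special website". The navigator demonstrates this on the family's phone if one is available and otherwise on the navigator's own, then goes to the diary calculator. No login, access code or study-ID link is mentioned.
- **Analysis.** Section 11 contains no criterion, summary or comparison that uses the tracking data.

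**The concern.** Website access is one of three conditions for calling the study feasible, and the pilot is meant to inform a later randomised trial. The measure that decides it is what parents tell the team that gave them the site. The plan also collects an objective measure that could test those answers, but two things are missing: a stated way to attribute a visit to a family, and a stated use for the log.

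The baseline demonstration adds to the problem. A parent whose phone was used to open the site during the nurse visit could truthfully say they had accessed it without ever returning. The same demonstration would appear in the log. The plan does not say whether it counts.

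If the survey is at Week 3, use in Weeks 4 to 12 is visible only in the log. Without linkage, the log cannot say how many families that use represents. Linkage has to be in place before visits occur, because it cannot be rebuilt from unlinked records.

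**Working it through.** The plan states no power, alpha or precision for this criterion, so there is no document figure to reproduce. The steps below size the issue.

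**1. The bar in families.** Inputs: N = 30 and the 50% bar (section 1.2). 0.50 × 30 = 15, so 15/30 passes and 14/30 (46.7%) fails. The exact (Clopper-Pearson) 95% interval at 15/30 is 31.3% to 68.7%.

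**2. The denominator.** The text says participants report, and only survey completers can report. At the plan's 80% completion bar, 0.80 × 30 = 24 complete.
- Denominator completers: 0.50 × 24 = 12 suffice (exact 95% interval 29.1% to 70.9%), and 12/30 = 40% of those enrolled.
- Denominator enrolled: 15 are needed, and 15/24 = 62.5% of completers.

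The plan does not say which applies.

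**3. What an unlinked log can show.** Section 11.2 gives 30 families in 12 months: 30/12 = 2.5 per month. Assuming even enrolment and 4.35 weeks per month, 12/4.35 = 2.76 months, and 2.5 × 2.76 = 6.9. About 7 families are therefore in their 12-week window at once. If visits are not linked, a total of 15 is compatible with 15 families (15/30 = 50%) or one family visiting 15 times (1/30 = 3%). Frequency and time of day do not separate these cases.

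**4. Sensitivity of the criterion to over-reporting.** The documents give no over-reporting rate, so f is an assumption shown over a range. Let p be the true share of families using the site. Assume every user reports use and a share f of non-users also does. The reported share is q = p + (1 − p)f, and the chance of passing is P(X ≥ 15) with X ~ Binomial(30, q).

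| True access p | f = 0 | f = 10% | f = 20% | f = 30% |
|---|---|---|---|---|
| 40%: q | 0.40 | 0.46 | 0.52 | 0.58 |
| 40%: chance of passing | 17.5% | 39.7% | 65.7% | 85.8% |
| 30%: q | 0.30 | 0.37 | 0.44 | 0.51 |
| 30%: chance of passing | 1.7% | 10.1% | 31.5% | 61.5% |

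Example: p = 0.40 and f = 0.20 give q = 0.40 + 0.60 × 0.20 = 0.52. Here f also stands for parents who truthfully count the nurse's demonstration as access.

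**5. The sections side by side.** Sections 1.2 and 11.5 define the criterion by report. Section 5.2 lists tracking under Feasibility, and section 5.6 words the website follow-up by participant, which suggests family-level data were intended. Appendices B and C describe how families reach the site but give no mechanism that would deliver such data. Section 11 gives the log no role.

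**The case against.** The strongest reply is that much of this is silence rather than error. A reader might infer that all families share one QR code and that visits therefore cannot be attributed to anyone. The documents do not support that. The action-plan artwork is not shown, nothing says the code is common to all families, and a printed bare address does not exclude a coded QR link. The participant-level wording in section 5.6 points the other way. What stands is narrower: no linkage is described.

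A reader might also conclude that a tracked visit should replace self-report as the criterion. That would be worse. The nurse opens the site from the plan's QR code at baseline, so a coded link could log a visit for nearly every family with no independent use.

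It is also fair to say that self-report is openly pre-specified, that reading the survey aloud is only an alternative mode, and that a single under-report is as decisive as a single over-report when N is 30. No over-reporting rate is given, so the table in the working shows sensitivity and does not show that bias exists. Section 11.5 calls the study feasible or not; it states no stop/go rule.

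None of this explains why a measure collected for 12 weeks under Feasibility has no stated unit, linkage or analysis.

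**Conclusion.** The point holds in limited form. The ≥50% website criterion depends on parent self-report alone, probably at Week 3, subject to reconciling the Week 12 sentence in section 5.2. The Week 1 to 12 log has no described link to families and no use in section 11. As described, it cannot show how many families used the site and cannot check the self-report. The baseline demonstration could inflate both measures.

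The decision turns on one family at 15/30, and an unstated denominator moves the bar between 12 and 15 families at 80% completion. Under the assumed reporting model, 20% over-reporting among non-users raises the chance of passing from 17.5% to 65.7% when true access is 40%. These figures rest on independent families, complete reporting by true users, a denominator of 30 and a value of f that the documents do not supply.

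The study can run as written. This is an inexpensive improvement that has to be made prospectively. It is not evidence that the log is anonymous or that the self-report is wrong.

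**What to change.** 1. Put a study-ID-coded QR code or short link on each family's action plan, leading to the same site, and disclose family-level tracking to families.
2. Keep self-report as the criterion, but word the item to ask about use after the nurse visit.
3. State that the criterion's denominator is enrolled families.
4. In sections 5.2 and 11.5, pre-specify reporting beside the criterion the number and proportion of enrolled families with at least one tracked visit after the day of the nurse demonstration. Give this up to the Intervention Assessment and up to Week 12, with the agreement between tracked and reported access.
5. Reconcile the Week 3 and Week 12 statements on when self-reported outcomes are collected.

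**Cost.** Thirty coded links, one reworded survey item and a short amendment covering the disclosure. Visits made by typing the bare address will be missed, and genuine visits on the demonstration day are excluded. Tracked access is therefore a lower bound, which is why it belongs beside the self-report and should not replace it. Fixing the denominator at enrolled families makes the criterion stricter when surveys are missing: 15 of 24 completers (62.5%) would have to report use at 80% completion.

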5.3 Agent Administration

N/A.

5.4 General Concomitant Medication and Supportive Care Guidelines

N/A.

5.5 Criteria for Taking a Participant Off Protocol Therapy

N/A.

5.6 Duration of Follow Up

Participants will be followed for 3-weeks after their initial ONN baseline visit for the Intervention survey; and a total of 12 weeks for any website activity.

5.7 Criteria for Taking a Participant Off Study

Participants will not be removed from study, unless they express a desire to do so.

6. DOSING DELAYS/DOSE MODIFICATIONS

N/A.

7. ADVERSE EVENTS: LIST AND REPORTING REQUIREMENTS

If families choose to implement behavioral strategies to try and improve their child's sleep, they may encounter brief periods of resistance from their child, as well as a brief period (<2 weeks) of further sleep disruption. This can create increased stress for families. However, the strategies described in the program materials are all evidence-based strategies that are commonly used in pediatric sleep centers to help children improve their sleep in the long-term, recognizing that there may be short-term challenges. In addition, there is a theoretical possibility of anxiety or emotional distress as a result of reviewing materials that discuss a common side effect of maintenance therapy (sleep disturbance). The emotional risk of anxiety as a result of discussing this topic is expected to be minimal based on data from prior qualitative research conducted with parents of pediatric cancer patients. Specifically, prior work on this topic has revealed that parents are often engaged in discussing this subject because they feel as though their experiences can help inform care for other parents who are going through the experience of having a child be diagnosed with cancer, and do not report significant stress or anxiety as a result of participation.

